14.1 Adverse events

PTSD Adverse Events are defined as a \geq 10 point rise in the self-report PCL-5 since the previous therapy session or a 15 point rise from baseline or the maximum score of 80 being reached and/or relapse into alcohol and/or substance misuse at a hazardous level which integrated with the clinical judgement of the treating therapist will determine the action taken.

Self-harm adverse events are defined as responding 1 or above on the PHQ-9, question 9 and

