2.0 Definitions related of safety

- 2.1 Mental health safety symptom severity, deterioration is assessed using the PCL-5 selfreport screening questionnaire completed by the participant at the beginning of every therapy session until discharge. Any existing or emergent safeguarding and or vulnerable adult concern will be assessed and monitored at each session with proportionate action taken in accordance with legislative reporting requirements.
- 2.2 Mental health safety is assessed using the PCL-5 and PHQ-9 (question 9) self-report screening questionnaires completed by the participant at the following time points following FIRST therapy discharge (intervention arm), or while awaiting therapy commencement at 20-weeks (control arm): 6 weeks post randomisation, 12 weeks post randomisation, 20 weeks post randomisation and 52 weeks post randomisation (for those in the intervention arm).
 - 2.2.1 The named researcher will review all incoming follow up PCL-5 and PHQ-9 scores within 72 hrs of receipt.
 - 2.2.2 If PHQ9, Q.9 (risk of self-harm) is scored 1-3 this will trigger a safety contact email correspondence from the assessors (see 4.0).
- 2.3 PTSD Adverse Events are defined as a ≥10 point rise in the self-report PCL-5 since the previous therapy session or a 15 point rise from baseline or the maximum score of 80 being reached and/or relapse into alcohol and/or substance misuse at a hazardous level which integrated with the clinical judgement of the treating therapist will determine the action taken.
- 2.4 The risk of Self-Harm Adverse Event is defined as when the research team has been unable to make contact with the participant (see 4.5) on three separate occasions and contact is made from the research team to the participant's GP.
- 2.5 PTSD Serious Adverse Events are defined as hospital admission for mental ill-health, self-harm, suicide and attempted or completed suicide.

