3.0 Safety net procedures for between therapy and follow up time points

- 3.1 All participants will be offered a *Contact Card* at the point of randomisation. This will list the contact details of services to call 24/7 if they feel they need to talk with someone about their mental health outside of their therapy session and throughout their trial participation. Contact details will include Lifeline, Samaritans and their GP and where appropriate their Aftercare case worker and Inspire's 24/7 helpline.
 - 3.1.1 For participants in therapy, the therapist will record participant self-reports of all contacts being made in the therapy safety log.
 - 3.1.2 For participants in follow up, the researcher will note such self-reports in the data collected and ask the participant for details. Details, if provided, will be recorded in the researcher's participant safety log.
 - 3.1.3 The unblinded researcher will review the therapy database weekly to determine if any activity has been logged in the previous seven days.

4.0 Care escalation procedures in the event of a risk of self-harm reported on the PHQ-9

- 4.1 If the participant self-reports thoughts of self-harm on the PHQ-9, by answering 1-3 on question 9, the safety contact communication will be triggered.
- 4.2 On identifying a score of 1-3 on Q9, the research team assessor will contact the participant to ask them about their response and to suggest they may wish to speak to their GP for support.
- 4.3 If the research team assessor is unable to make contact or do not hear back from the participant within 24 hours, they will send a follow-up email.

- 4.4 If research team assessor still receive no response, they will send a third communication saying they have emailed the participant twice over the past two days and if they do not hear from them within 24 hours they will get in touch with their GP to let them know that they are concerned about them.
- 4.5 If this final communication does not elicit a response, the research team assessor will escalate the reporting and contact the GP, to voice our concerns. This will be reported to one of the study's senior investigators ([name] or [name]) and be registered as an adverse event.

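### Appendix 1 registers a self-harm adverse event only on failed contact, so its count mixes the risk of self-harm thoughts with non-response

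*Protocol*

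**What the plan says.** Appendix 1, 2.4 gives the definition: "The risk of Self-Harm Adverse Event is defined as when the research team has been unable to make contact with the participant". It requires three separate failures, followed by contact with the GP, and refers to 4.5 for the procedure.

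Appendix 1, 4.0 sets out that procedure:

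- 4.1, the trigger: "If the participant self-reports thoughts of self-harm on the PHQ-9, by answering 1-3 on question 9, the safety contact communication will be triggered".
- 4.2, the first step: "the research team assessor will contact the participant to ask them about their response and to suggest they may wish to speak to their GP".
- 4.3 and 4.4: a second and then a third message if nothing is heard.
- 4.5, the end of the sequence: "If this final communication does not elicit a response, the research team assessor will escalate the reporting and contact the GP, to voice our concerns". A senior investigator is told, and the case will "be registered as an adverse event".

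Section 14.1 in the main body begins from the score: "Self-harm adverse events are defined as responding 1 or above on the PHQ-9, question 9 and". The sentence stops there in the text at hand.

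Appendix 1, 2.5 covers the graver outcomes, with no condition on contact: "PTSD Serious Adverse Events are defined as hospital admission for mental ill-health, self-harm, suicide and attempted or completed suicide". Section 14.2 says the same.

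Section 8.10.2 says that an escalation of symptoms in a waiting list participant will be picked up and recorded as an adverse event, and cites Appendix 1 as the means. Section 14, Table 7 and Appendix 1, 2.2 together show that the PHQ-9 is collected at baseline and at 6, 12 and 20 weeks in both arms, and at 52 weeks in the FIRST arm.

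**The concern.** An adverse event definition should turn on what happened to the participant. This one turns on whether the participant answers the research team. Under Appendix 1, someone who scores 3 on question 9, replies and confirms the thoughts is not registered. Someone who scores 1 and misses three messages is.

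Waiting list safety is one of the things the internal pilot monitors (section 10.7). Adverse events go into the TSC reporting (section 14.3), and the DMEC assesses safety and advises the TSC (section 12.4). If these bodies read the registered events as the record of self-harm thoughts, they see a figure that falls when contact works well and rises when it works badly. Section 8.10.2 rests its assurance about the waiting list arm on this same appendix.

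**Working it through.** No stated figure depends on this rule, so the check is mainly a comparison of the provisions.

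**Step 1. Outcomes under Appendix 1, 4.0 for a question 9 score of 1-3.**

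| Participant | Provision reached | Registered as an adverse event? |
|---|---|---|
| Replies to the first, second or third message | 4.2 to 4.4 | No registration step |
| Replies to none | 4.5 | Yes |

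The size of the score (1, 2 or 3) and the content of the reply play no part. Section 2.4 agrees, since it names failed contact and not the score.

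**Step 2. Comparison with the PTSD adverse event.** Appendix 1, 2.3 defines that event mainly by PCL-5 scores: a rise of 10 or more since the previous session, a 15-point rise from baseline, or the maximum of 80. Reply to a message is not part of it. Non-response makes the event only in the self-harm definition.

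**Step 3. Comparison with section 8.10.2.** A waiting list participant whose question 9 response goes from 0 at baseline to 2 at week 12, and who replies, has escalated. Appendix 1, 4.0 registers nothing for this participant, so for self-harm thoughts in those who reply, the appendix does not do what 8.10.2 says it does.

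**Step 4. What the count measures.** Let n be the number per arm, q the share scoring 1 or more on question 9, and u the share of those who answer none of the three contacts.

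- Positive responses = n × q
- Registered events = n × q × u
- Share of positive responses not registered = 1 − u

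With 215 randomised 1:1, n is about 107. The documents give neither q nor u, so all values below are assumptions.

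| q | n × q | Registered, u = 5% | Registered, u = 30% |
|---|---|---|---|
| 20% | 21.4 | 1.1 | 6.4 |
| 40% | 42.8 | 2.1 | 12.8 |
| 60% | 64.2 | 3.2 | 19.3 |

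Whatever q is, between 1 − 0.30 = 70% and 1 − 0.05 = 95% of positive responses go unregistered over this range of u.

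**Step 5. Possible effect on a comparison of arms.** Registered rate = q × u.

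- Same risk, different reply: q = 40% in both arms, u = 5% against 20%. Rates are 0.40 × 0.05 = 2% and 0.40 × 0.20 = 8%, a fourfold gap with no difference in risk.
- Different risk, different reply: q = 60% against 30%, u = 5% against 10%. Rates are 0.60 × 0.05 = 3% and 0.30 × 0.10 = 3%, which hides a twofold difference.

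These cases show that the count could create or conceal a difference. They do not show that it will in this trial.

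**The case against.** The case against a strong reading is good, and much of it stands.

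- **Self-harm is not missed.** A reader might infer that self-harm itself goes uncounted. Acts, attempts, suicide and mental-health admissions are SAEs whatever the contact status, and the DMEC chair is told of each within 24 hours (section 14.3; Appendix 1, 6.3). The gap is limited to thoughts reported on question 9.
- **"Never counted" cannot be shown.** Section 14.1 also defines the event and starts from the score. Its second condition is lost in the text at hand. It may count every positive score, or it may repeat the failed-contact condition. A contradiction between 14.1 and Appendix 1 is therefore unproven, and the cut-off is not an error in the plan.
- **The DMEC can see the scores.** It has unmasked access to all data (section 12.4), and question 9 is collected in both arms, so the responses can be tabulated by arm whatever is called an event. This makes the problem easy to correct, but it does not repair the definition in 2.4 and 4.5.
- **The count is not pure contactability.** In section 4.0 a registered case first needs a score of 1-3, so the count is risk times non-response. The protocol specifies no formal comparison of adverse events between arms.
- **Different reply rates by arm are conjecture.** One might expect FIRST participants to reply more because they have been in therapy. But the messages come from research assessors in both arms. Therapy starts within three weeks and lasts at most four, so it should be over by about week 7, before the 12- and 20-week assessments. Waiting list participants expecting therapy could be just as responsive.
- **Baseline matters.** Thoughts already present at entry are not an escalation. Counting every later positive response as a new event would overstate change.

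None of these points supplies a registration step in Appendix 1 for the participant who replies.

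**Conclusion.** The point holds in a limited form. Under Appendix 1, 2.4 and 4.5, the self-harm adverse event is registered on failure to answer three contacts, and a participant who replies and confirms self-harm thoughts is not registered there. The resulting count is risk multiplied by non-response, and it falls short of the assurance in section 8.10.2. This follows from the stated rule and does not depend on detail left to a SAP.

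Its size cannot be taken from the documents. Under the assumed non-response of 5% to 30%, 70% to 95% of positive responses would go unregistered. The direction and size of any arm difference are unknown, and the fourfold and hidden twofold differences are illustrations only. The documents do not support saying that confirmed thoughts are counted nowhere, that 14.1 contradicts Appendix 1, or that a comparison of arms would measure contactability alone. The primary analysis is not affected.

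**What to change.** Reconcile section 14.1 with Appendix 1, 2.4 and 4.5, so that one definition applies throughout and self-harm event reporting to the DMEC does not depend on whether the participant replies. For that reporting:

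- tabulate question 9 responses by arm at 6, 12 and 20 weeks alongside the baseline response, so that thoughts present at entry can be told apart from new or worse ones;
- log failed contact as a separate item.

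The contact and GP steps stay unchanged; this concerns only what is counted and reported.

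The cost is a change of wording and a short table. The PHQ-9 is already collected at these times in both arms, so no new data are needed. The downside is a longer event listing for the DMEC.

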3.0 Safety net procedures for between therapy and follow up time points

- 3.1 All participants will be offered a *Contact Card* at the point of randomisation. This will list the contact details of services to call 24/7 if they feel they need to talk with someone about their mental health outside of their therapy session and throughout their trial participation. Contact details will include Lifeline, Samaritans and their GP and where appropriate their Aftercare case worker and Inspire's 24/7 helpline.
 - 3.1.1 For participants in therapy, the therapist will record participant self-reports of all contacts being made in the therapy safety log.
 - 3.1.2 For participants in follow up, the researcher will note such self-reports in the data collected and ask the participant for details. Details, if provided, will be recorded in the researcher's participant safety log.
 - 3.1.3 The unblinded researcher will review the therapy database weekly to determine if any activity has been logged in the previous seven days.

4.0 Care escalation procedures in the event of a risk of self-harm reported on the PHQ-9

- 4.1 If the participant self-reports thoughts of self-harm on the PHQ-9, by answering 1-3 on question 9, the safety contact communication will be triggered.
- 4.2 On identifying a score of 1-3 on Q9, the research team assessor will contact the participant to ask them about their response and to suggest they may wish to speak to their GP for support.
- 4.3 If the research team assessor is unable to make contact or do not hear back from the participant within 24 hours, they will send a follow-up email.

- 4.4 If research team assessor still receive no response, they will send a third communication saying they have emailed the participant twice over the past two days and if they do not hear from them within 24 hours they will get in touch with their GP to let them know that they are concerned about them.
- 4.5 If this final communication does not elicit a response, the research team assessor will escalate the reporting and contact the GP, to voice our concerns. This will be reported to one of the study's senior investigators ([name] or [name]) and be registered as an adverse event.

5.0 Care escalation procedures in the case of adverse event

- 5.1 If at point of referral or during the course of treatment, Inspire therapists become concerned about the welfare of any participant or immediate family member they will escalate their concerns through Inspire's standardised risk assessment, escalation, management and safeguarding policies and procedures. Where necessary they will contact the participant's GP to mobilise referral to crisis response, NHS primary or secondary care. Likewise, if a safeguarding and vulnerable adults concern is identified this will be escalated, acted on and reported to the relevant statutory body safeguarding team.
 - 5.1.1 The PCL- 5 will be completed at each therapy session. If ≥10 point rise in PCL-5 score occurs since the previous therapy session, or 15-point rise from baseline, or the maximum score of 80 is recorded on the PCL-5, they will use their clinical judgement to assess whether escalation is appropriate.
 - 5.1.2 Any ≥10 point rise in PCL-5 score that occurs since the previous therapy session, or 15-point rise from baseline, or the maximum score of 80 recorded on the PCL-5, will be detected by the unblinded member of the research team (investigator [name]) who will inform the DMEC chair within three working days.
- 5.2 If a participant's PCL-5 score rises by ≥10 points from the previous follow up, or 15point rise from baseline, or the maximum score of 80 is recorded on the PCL5, the unblinded researcher (investigator [name]) will make contact with the participant within six hours of noting the rise in score and encourage them to contact their GP and/or their case worker. They will advise the participant that the researcher will need to contact the participant's case worker (or GP if no case worker) to alert them to the rise in PTSD symptoms.

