14.3 Care escalation procedures

If the participant is in therapy, Inspire will hold responsibility and clinical governance accountability for the participant's mental health and wellbeing, including their own safety and where relevant the safety of others and including the safeguarding of children and vulnerable adults. If at point of referral or during the course of treatment, Inspire therapists become concerned about the welfare of any participant or immediate family member they will escalate their concerns through Inspire's standardised risk assessment, escalation, management and safeguarding policies and procedures. Where necessary they will contact the participant's GP to mobilise referral to crisis response, NHS primary or secondary care. Likewise, if a safeguarding and vulnerable adults concern is identified this will be escalated, acted on and reported to the relevant statutory body – safeguarding team.

Before the participant is referred to Inspire and after discharge, the participant's GP holds responsibility and accountability for the participant's mental health and wellbeing and this includes their safety. If the participant scores on the PCL-5 indicate an adverse event, the unmasked researcher responsible for participant safety will make contact with the participant within six hours of noting the rise in score and encourage them to contact their GP and/or case worker. They will advise the participant that they will need to contact the participants GP and/or case worker to alert them to the rise in PTSD symptoms. The research team will review all incoming follow-up PCL-5 and PHQ-9 scores within 72 hours of receipt.

All AE will be recorded and reported to the study PI within 72 hours and will be discussed at the biweekly research core-team sub-group meeting. A report will be included in the TSC reporting for review.

A Serious Adverse Event that occurs following discharge from Inspire but whilst in the trial will be investigated by one of the study's senior investigators (i.e. [name] or [name]) using Inspire's SAE investigational policies and procedures. The investigational report will be submitted to the DMEC chair.

The DMEC chair will be notified within 24 hours of the research team being notified of all serious adverse events.

All AE and SAE and the clinical and research team actions will be logged in the Trial Management File.

15 Ethics and regulatory approvals

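### The PCL-5 adverse-event definition has no 10-point limb measured from the previous follow-up, so waiting-list rises that Appendix 1, 5.2 acts on need not be recorded as adverse events

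*Protocol*

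**What the plan says.** Four places in the protocol bear on the same PCL-5 score.

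- **Definition.** Appendix 1, 2.3 reads "PTSD Adverse Events are defined as a ≥10 point rise in the self-report PCL-5 since the previous therapy session". Its alternatives are a 15-point rise from baseline, a score of 80, and relapse into hazardous alcohol or substance use. Section 14.1 has the same limbs: "point rise in the self-report PCL-5 since the previous therapy session or a 15 point rise from baseline".
- **Action outside therapy, Appendix 1.** Section 5.0 is headed "Care escalation procedures in the case of adverse event". Within it, 5.2 covers follow-up scores and begins "If a participant's PCL-5 score rises by ≥10 points from the previous follow up". It adds the same 15-point and score-80 limbs and requires contact within six hours.
- **Action outside therapy, main text.** Section 14.3 prescribes the same six-hour contact, introduced by "If the participant scores on the PCL-5 indicate an adverse event". It also requires every adverse event to be recorded, reported to the PI within 72 hours, and covered in the report to the TSC.
- **Statement about the control arm.** Section 8.10.2, citing Appendix 1, says that any worsening of symptoms on the waiting list will be picked up and logged as an adverse event.

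Waiting-list participants start FIRST only after the 20-week data collection (8.6, 8.10.2). Appendix 1, 2.2 gives the safety time points as "6 weeks post randomisation, 12 weeks post randomisation, 20 weeks post randomisation and 52 weeks post randomisation", the last of these for the intervention arm only.

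**The concern.** The 10-point limb of the definition was written for people in therapy: it compares one session with the one before. A waiting-list participant has no session to compare with until the 20-week assessment is complete, so for that arm the limb cannot operate at weeks 6, 12 or 20. Section 5.2 supplies the missing comparison, follow-up to follow-up, but only as a trigger for contact. The definition was not extended to match.

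Two things are at stake. First, staff who make contact under 5.2 have no defined adverse event to log, so the event need not reach the PI or the TSC as one, and what 8.10.2 says of this arm is not delivered. The internal pilot is meant to monitor waiting-list safety (10.7), and the DMEC is responsible for assessing safety (12.4). Second, before week 20 the session-based limb can be met only in the therapy arm. A comparison of PCL-5 adverse events between arms would therefore apply a narrower definition to the waiting list.

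**Working it through.** No published figure has to be reproduced. The check applies each rule literally to a waiting-list participant.

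**Inputs.** Definition: 14.1 and Appendix 1, 2.3. Contact rule: Appendix 1, 5.2. Visits before therapy: weeks 6, 12 and 20 (Appendix 1, 2.2). Illustrative baseline: 57, the feasibility-trial mean (5.5).

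**Rules before therapy.** Let b be the baseline score, p the score at the previous follow-up and s the current score.

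- Adverse event under 14.1/2.3 on PCL-5 grounds: s − b ≥ 15, or s = 80. The session limb is empty.
- Contact under 5.2: s − p ≥ 10, or s − b ≥ 15, or s = 80.

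The two disagree when p + 10 ≤ s ≤ b + 14 and s ≤ 79.

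**Worked paths with b = 57, week 6 then week 12.**

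| Week 6 | Week 12 | From previous follow-up | From baseline | Contact under 5.2 | Adverse event under 14.1/2.3 |
|---|---|---|---|---|---|
| 57 | 68 | 68 − 57 = 11 | 68 − 57 = 11 | yes | no |
| 55 | 65 | 65 − 55 = 10 | 65 − 57 = 8 | yes | no |
| 50 | 64 | 64 − 50 = 14 | 64 − 57 = 7 | yes | no |
| 57 | 72 | 72 − 57 = 15 | 72 − 57 = 15 | yes | yes |

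**Width of the disagreement with b = 57.** The upper limit is 57 + 14 = 71. The week-12 scores on which the rules split are:

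- week 6 = 50: scores 60 to 71, which is 12 scores;
- week 6 = 55: 65 to 71, which is 7;
- week 6 = 57: 67 to 71, which is 5;
- week 6 = 60: 70 and 71, which is 2;
- week 6 = 61: 71 only, which is 1;
- week 6 = 62 or more: none, because 62 + 10 = 72 already meets the 15-point limb.

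The same calculation holds at week 20 with week 12 as the previous follow-up. The split is widest for people who improved a little and then worsened.

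**Week 6.** Week 6 is the first listed follow-up. Read literally, 5.2 has no previous follow-up to use there, so both rules reduce to 15 from baseline or a score of 80. At b = 57 both start at 72, so the two rules agree at this visit.

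**Number affected.** The protocol gives no distribution of PCL-5 changes on a waiting list, so the number of participants cannot be derived.

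**The case against.** The strongest reply is that the text can be harmonised. Sections 5.1.1 and 5.1.2 govern sessions during therapy, 5.2 governs follow-ups outside it, and all three sit under a heading about adverse events. On that reading a 5.2 trigger is an adverse event, and the definition merely lacks a phrase. This is probably what was intended. It does not remove the defect: 2.3 and 14.1 are the passages that say what an adverse event is, and they do not include the 5.2 trigger.

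Three stronger readings are tempting, and the protocol does not support them.

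- *Section 14.3 tells staff not to make contact.* It says what to do when scores indicate an adverse event. It does not confine contact to that case, so staff who follow 5.2 breach nothing. The conflict concerns recording and reporting; contact itself is not prohibited anywhere.
- *A rise of 10 to 14 points at week 6 is an erroneous gap.* Read literally, 5.2 gives a clear week-6 rule of 15 points from baseline or a score of 80, and a two-tier rule may be deliberate. The 10-point MCID in 10.8.1 is an outcome benchmark, and the protocol does not make it the safety threshold from baseline. Section 14 does list baseline among the data collection time points, so the wording is worth clarifying, but it is not an error.
- *The waiting list is unmonitored.* The 15-point and score-80 limbs operate at every follow-up. PHQ-9 item 9, the 72-hour score review, the contact card, GP responsibility and the fortnightly safety review also apply.

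**Conclusion.** Wrong as written, with minor severity. For a waiting-list participant, a PCL-5 rise of 10 or more from week 6 to 12, or from week 12 to 20, that stays less than 15 above baseline and below 80 triggers contact under 5.2. It is not a PCL-5 adverse event under 14.1 or 2.3, so it lies outside the reporting that 14.3 attaches to adverse events and contradicts 8.10.2. At a baseline of 57 this covers up to 12 week-12 scores in the cases worked above, and none once the week-6 score reaches 62.

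Before week 20, PCL-5 adverse-event counts are not like for like between arms, because only the therapy arm can meet the session limb.

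The conclusion rests on a literal reading of the definition and on the absence of therapy sessions before week 20 in the control arm. A participant could still have an adverse event recorded on other grounds, such as substance relapse. No efficacy analysis, sample size or power is affected, and no missed harm is shown.

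**What to change.** In 14.1 and Appendix 1, 2.3, extend the 10-point limb so that the rise is measured from the last therapy session or, outside therapy, from the previous follow-up. Keep the 15-from-baseline and score-80 limbs. Leave 5.1.1 and 5.1.2 unchanged: they already agree with the definition for people in therapy, and widening them would add DMEC notifications for no gain. Section 14.3 then works without its own edit.

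As a clarification only, state in 5.2 whether baseline counts as the previous follow-up at week 6. If it does not, the week-6 trigger is 15 points or a score of 80, and 8.10.2 should be worded to match.

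The cost is one phrase in two places, a sentence in 5.2 and possibly a rewording of 8.10.2. The scores are already collected. The downside is some more recorded adverse events, with the PI and TSC reporting that follows, and some of these will be fluctuation rather than deterioration. The change aligns the definition across arms. It does not equalise the number of PCL-5 measurements, since the therapy arm is also scored before each session.
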